### **5.4.2 *Adrenal suppression***

Asymptomatic subjects without clinical signs of adrenal insufficiency and abnormal ACTH and/or cortisol test results at the end of the intervention period may be observed without steroid replacement and retested in 1 month. In case of development of symptoms suggestive of adrenal suppression (such as abdominal pain, nausea and vomiting, fatigue and hypotension) subjects will then be placed on the standard maintenance replacement regimen of the corticosteroids such prednisone 5-7.5 mg once daily and reevaluated in 1 month

by ACTH testing. All subjects with the abnormal ACTH test results will be advised of the symptoms and signs of clinically significant adrenal suppression and will be given stress doses of hydrocortisone injections for emergencies and a wrist bracelet.

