#### 8.4.6 Assessment of adrenocortical function (cortisol levels)

Subjects will be evaluated for possible hypothalamic-pituitary axis (HPA) axis suppression with the following measures:

1. Morning cortisol levels will be determined at baseline, monthly follow-ups (done at NIH), and at completion of the interventional phase (3 months after the last dose of study medication). The results will be blinded to the investigators until the end of the study. At the end of the study, in subjects with morning cortisol levels between 19 mcg/dL and 3 mcg/dL no further adrenal function testing will be performed.
2. In subjects with the symptoms of suspected adrenal insufficiency, a Short Cosynthropicin Test (SCT) will be performed to determine if the subject has HPA axis suppression. In brief: venous blood will be collected before administration of 250 mcg of cosyntropicin (synthetic ACTH) around 8 AM to 12 noon, and at 30 and 60 minutes after. The expected rise in cortisol levels is to at least 18 mcg/dL (24). In cases of minimally abnormal SCT (stimulated cortisol values of 13-17 mcg/dL), the test will be repeated the next day, as it has been demonstrated that the result is often normal with a repeat test. This test has been shown to be sensitive and specific for evaluation of subclinical adrenal suppression [52, 53]. In the unlikely event of significant adrenal suppression as assessed by repeat ACTH stimulation test, Clinical Center Endocrinology Service will be consulted. Pharmacy will be requested to unblind therapy to the endocrinologist so that appropriate therapy can be initiated and the endocrinologist can appropriately attribute the relationship of the event to study drug administration.
3. The confounding effect of systemic corticosteroids will be taken into account at the time of analysis. We expect to have a subgroup of subjects who will not receive systemic steroids. This subgroup will be used to evaluate the effects of topical dexamethasone on adrenal secretion.

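### For a subject with an abnormal adrenal result who becomes symptomatic, 5.4.2 starts replacement and tests a month later, while 8.4.6 tests first and, for significant suppression, involves an unblinded endocrinologist before therapy

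*Combined protocol and SAP*

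**What the plan says.** Section 5.4.2 (Adrenal suppression) begins with subjects who have no symptoms but an abnormal ACTH and/or cortisol result when the intervention ends. They "may be observed without steroid replacement and retested in 1 month". It then turns to symptoms: "In case of development of symptoms suggestive of adrenal suppression", it says, "subjects will then be placed on the standard maintenance replacement regimen", for example "prednisone 5-7.5 mg once daily and reevaluated in 1 month", the re-evaluation being by ACTH testing.

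Section 8.4.6 item 2 also starts from symptoms. A short cosyntropin test "will be performed to determine if the subject has HPA axis suppression", with an expected stimulated cortisol of at least 18 mcg/dL. "In cases of minimally abnormal SCT (stimulated cortisol values of 13-17 mcg/dL), the test will be repeated the next day". If the repeat test shows significant suppression, the endocrinology service is consulted and "Pharmacy will be requested to unblind therapy to the endocrinologist so that appropriate therapy can be initiated".

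Three other places bear on this. Section 8.4.6 item 1 withholds cortisol results from investigators until the study ends, and 6.3 also marks the three-month cortisol as blinded. Section 6.3 lists the ACTH stimulation test at three months as optional. Section 10.3.1 restates the consultation rule and points to 8.4.6, not to 5.4.2.

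**The concern.** The two sections put treatment and testing in opposite orders for a subject in the same clinical state. In 5.4.2 replacement comes first and the ACTH test a month later. In 8.4.6 the test comes first, and the route it describes to therapy runs through endocrinology. Nothing tells site staff which section governs.

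Section 10.3.1 describes the symptoms as non-specific and very common among hospital patients. A rule triggered by symptoms and a rule triggered by a test result can therefore pick out different people.

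Two things are at stake for the trial:

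- **Steroid exposure.** Section 8.4.6 item 3 names systemic corticosteroids as a confounder of the adrenal analysis, which serves secondary objective 1.2.3. Replacement is such an exposure, and whether it is given depends on the section followed.
- **Disclosure of the arm.** Section 4.3 keeps investigators and subjects blinded to the end of the study. Section 8.4.6 provides for telling the endocrinologist the assignment; 5.4.2 provides for no disclosure.

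Subject safety is also involved, because a protocol with two different sequences cannot be applied consistently.

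**Working it through.** No figure in the plan needs reproducing and no arithmetic applies. The check is a comparison of the two rules.

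| Step | 5.4.2 | 8.4.6 item 2 |
|---|---|---|
| Entry | Symptoms, following a sentence about subjects with an abnormal end-of-intervention result | Symptoms, with no condition on earlier results |
| First action | Replacement corticosteroid | Short cosyntropin test |
| Next-day repeat | Not named | Only for stimulated values of 13-17 mcg/dL |
| Endocrine consultation | Not named | For significant suppression on the repeat test |
| Unblinding | Not named | To the endocrinologist, ahead of therapy |
| Later test | ACTH test at 1 month | Not named |

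1. **Abnormal result at end of intervention, then symptoms.** Section 5.4.2 applies on any reading and leads straight to replacement. Section 8.4.6 item 2 also applies, since it makes no exception for subjects already found abnormal. If the cosyntropin test reaches the expected 18 mcg/dL, 8.4.6 has no therapy step. If suppression is significant on repeat, consultation and disclosure to the endocrinologist come before therapy. The same subject may be treated under one section and not the other, or treated by different routes.

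2. **Symptoms with no earlier test.** Section 8.4.6 calls for the cosyntropin test. Section 5.4.2 calls for replacement if its symptom sentence stands alone, and is silent if that sentence continues the one before it. The conflict in this case depends on the reading.

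3. **Can 5.4.2 be carried out?** It acts on abnormal ACTH and/or cortisol results. The cortisol result is withheld from investigators, and the documents name no one who reviews it during the study and passes it on. The three-month ACTH test is optional. For a subject who declines it, cortisol is the only result left, and the investigator does not see it. If that value did reach someone, 5.4.2 could bring the subject to replacement without a stimulation test ever having been done.

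4. **A gap inside 8.4.6.** The repeat is ordered only for values of 13-17 mcg/dL, but consultation depends on a repeat test. A first value below 13 mcg/dL has no stated next step.

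5. **Cross-references.** Neither 5.4.2 nor 8.4.6 mentions the other, and 10.3.1 leads only to 8.4.6. A reader starting in the treatment plan and a reader starting in the risk section arrive at different rules.

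**The case against.** The strongest defence is that 5.4.2 manages a known complication while 8.4.6 assesses whether there is one, as their headings suggest. The word then in 5.4.2 follows a sentence about subjects already tested, abnormal and under observation. On that reading, 5.4.2 does not treat anyone on symptoms alone. This stands as a fair reading, and it removes the conflict for subjects with no earlier test. It does not remove case 1, because 8.4.6 item 2 covers all symptomatic subjects and its test, consultation and disclosure steps are still missing from 5.4.2.

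Four stronger inferences are tempting, and the documents do not support them.

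- A reader might infer a second conflict for subjects without symptoms: a one-month wait in 5.4.2 against a next-day repeat in 8.4.6. The repeat rule sits inside an item that opens with symptomatic subjects, so on its placement it does not govern the others. The two intervals also serve different purposes: one confirms a borderline test, the other re-evaluates an observed or treated subject.
- A reader might infer that 8.4.6 breaks the blind generally. It discloses the arm to the endocrinologist only, and only for significant suppression on a repeat test.
- A reader might want to put a percentage on the difference in treated subjects. Section 8.4.6 says only that repeat tests are often normal, and says it of minimally abnormal results. It gives no rate and says nothing about lower values or about cortisol alone.
- A reader might infer that replacement steroids would confound the late oral GVHD follow-up. No passage shows that replacement dosing affects new onset, and the systemic corticosteroids section under 2.4 calls systemic corticosteroids ineffective for GVHD prevention. Steroid use is already tracked under 5.2.2, and 8.5 plans stratified analyses for systemic immunosuppressive agents.

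**Conclusion.** The point holds as an internal inconsistency. For a symptomatic subject with an abnormal end-of-intervention ACTH and/or cortisol result, 5.4.2 and 8.4.6 item 2 cannot both be followed as written. For a symptomatic subject without such a result, they conflict only if 5.4.2's symptom sentence is read on its own. Section 5.4.2 also depends on information that 6.3 and 8.4.6 item 1 withhold or make optional.

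The consequence is limited to who receives a systemic corticosteroid, by what route and when, and whether the endocrinologist learns the arm. The number of subjects cannot be derived from the documents; 8.4.6 and 10.3.1 both call significant suppression unlikely. No effect on the primary endpoint or the sample size is shown. For subjects found abnormal when the intervention ends, any replacement under 5.4.2 comes after the three-month assessment.

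The case for correcting it rests on safety, consistent conduct and an interpretable adrenal analysis. The conclusion assumes only that both sections are in force in the current protocol, and nothing in the text says that one overrides the other.

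**What to change.** Reconcile 5.4.2, 6.3, 8.4.6 and 10.3.1 into one adrenal pathway, agreed with the endocrinology service, placed in one section and cross-referenced from the others. It should state:

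- which subjects enter it, and whether an earlier abnormal result is required;
- the order of testing, consultation, disclosure of the arm and any replacement;
- what follows a first stimulated value below 13 mcg/dL;
- who sees the blinded cortisol results during the study, and how an abnormal one reaches whoever must act on it;
- what happens when the optional ACTH test was not done.

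Which clinical rule is adopted is for the sponsor and the endocrinology service; no view is taken here. The cost is protocol wording and one agreement with that service. No new data collection is needed to record replacement, since systemic steroid use is already tracked under 5.2.2.

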#### ***Other complications***

Other complications attributable to the medications or procedures used in this study such as allergic reactions will be managed in accordance with the currently accepted standards of care.

## **6. CLINICAL MONITORING AND ASSESSMENTS**

### **6.1 Pre-study Evaluation and Assessments**

#### **6.1.1 Eligibility assessment**

Subjects will be screened for eligibility between days 60 and 90 post transplant using the following assessments which are done under the subject's parent transplant protocol or the NHLBI screening protocol 1997-H-0041:

- Review of medical history
- Review of concomitant meds
- Blood pressure
- Complete oral examination
- Complete blood count (CBC with diff) –done concurrently with post transplant monitoring
- Consent if eligible and randomization

#### **6.1.2 Baseline assessments**

- Serum chemistry (Acute Care (Na, K, Cl, CO2, Creatinine, Glucose, and Urea Nitrogen), Mineral (Phosphorus, Magnesium, Albumin, and Calcium), Hepatic (Alk Phosphatase, ALT, AST, Total Bilirubin, and Direct Bilirubin), and Other (Total Protein, CK, Uric Acid, and LD) panel) done concurrently with post transplant monitoring
- Pregnancy test (females of child bearing potential)
- Serum cortisol level (results blinded to investigators)
- The 0-10 Scale for Oral Pain (see Appendix A)
- The 0-10 Scale for Oral Xerostomia (see Appendix A)
- GVHD Severity Scale (see Appendix B)
- Lichen Planus (Oral GVHD) Severity Scale (see Appendix C)
- Disease specific quality of life - OHIP-14 scale (ages 18 and older only-Appendix D)
- Oral photographs (Optional)
- Oral lesion documentation
- Buccal mucosal less than approximately 6mm punch biopsy (ages 18 and older only) (optional)
- Research blood sample collection
- Research saliva sample collection
- Growth chart (length for age, weight for age percentiles and body mass index for age percentiles, pre-pubertal children) (if a hand x-ray is available on parent transplant protocol, the results will be reviewed)

### **6.2 On Study Drug Interim Assessments (1 month and 2 month phone contact)**

The NIH research team will contact the subject by clinical appointment, telephone or email at 1 month and 2 months (+/- 2 weeks) after initiation of study drug to inquire about adverse effects and the use of concurrent medications. Laboratory assessments done as part of their post transplant monitoring will also be reviewed when available. Subjects will be asked to return to clinic when clinically indicated and the following questionnaires will be completed at the time of contact.

- Concomitant meds (immunosuppressive, antimicrobial and analgesics)
- The 0-10 Scale for Oral Pain (see Appendix A)
- The 0-10 Scale for Oral Xerostomia (see Appendix A)
- Patient-assessed Global Scale (perception of changes in oral condition)

### **6.3 End of Treatment Monitoring and Assessments (3 months)**

Subjects will be evaluated at the NIH at 3 months (+/- 7 days) after starting study medication with the following assessments:

- Interim assessment
- Blood pressure
- Concomitant meds (immunosuppressive, antimicrobial and analgesics)
- The 0-10 Scale for Oral Pain (see Appendix A)
- The 0-10 Scale for Oral Xerostomia (see Appendix A)
- Patient-assessed Global Scale (perception of changes in oral condition-Appendix A)
- GVHD Severity Scale (see Appendix B)
- Lichen Planus (oral GVHD) Severity Scale (see Appendix C)
- Disease specific QOL- OHIP-14 scale (ages 18 and older only) (Appendix D)
- Complete blood count (CBC with diff) – done concurrently with post transplant monitoring
- Serum chemistry (Acute Care (Na, K, Cl, CO2, Creatinine, Glucose, and Urea Nitrogen), Mineral (Phosphorus, Magnesium, Albumin, and Calcium), Hepatic (Alk Phosphatase, ALT, AST, Total Bilirubin, and Direct Bilirubin), and Other (Total Protein, CK, Uric Acid, and LD) panel) – done concurrently with post transplant monitoring
- Serum cortisol level (results blinded to investigators)
- ACTH stimulation test (Optional)
- Serum dexamethasone level (results blinded to the investigators)
- Buccal mucosal less than approximately 6mm punch biopsy ages 18 and older only (optional)
- Oral photographs (Optional)
- Oral lesion documentation
- Research blood sample collection
- Saliva sample collection
- Growth chart (length for age, weight for age percentiles and body mass index for age percentiles, pre-pubertal children) (if hand x-ray is available on parent transplant protocol, the results will be reviewed)

### **6.4 Follow-up Remote Assessment**

If available, after completion of study drug, subjects will be contacted by clinic appointment, phone or email monthly +/- 2 weeks for 5 months: Months 4, 5, 6, 7, and 8. Subjects will be asked to report any symptoms or signs consistent with oral chronic GVHD. In addition, the monthly follow-up remote visits will be used to confirm the absence of oral chronic GVHD symptoms (oral discomfort and xerostomia) and collect the information about the current use of medications. If subject reports symptoms or signs consistent with oral

chronic GVHD, the following will be performed at the time of contact:

- Concomitant meds (immunosuppressive, antimicrobial and analgesics)
- The 0-10 Scale for Oral Pain (see Appendix A)
- The 0-10 Scale for Oral Xerostomia (see Appendix A)
- Patient-assessed Global Scale (perception of changes in oral condition)

## **6.5 End of Study Assessments (6 months after initiation of oral dexamethasone or diagnosed with oral chronic GVHD)**

After completion of 6 months of follow up, or in the event of symptoms or signs suggestive of oral chronic GVHD, or in case of premature withdrawal from the study and discontinuation of study drug, subjects will return to the Clinical Center for the following end of study assessments:

- Interim assessment including use of immunosuppressive, antimicrobial and analgesic medications
- The 0-10 Scale for Oral pain (see Appendix A)
- The 0-10 Scale for Oral Xerostomia (see Appendix A)
- GVHD Severity Scale (see Appendix B)
- Lichen Planus (Oral GVHD) Severity Scale (see Appendix C)
- Disease specific quality of life - OHIP-14 scale (ages 18 and older only-Appendix D)
- Patient-assessed Global Scale (perception of changes in oral condition)
- Buccal mucosal less than approximately 6mm punch biopsy (18 years or older and if clinically indicated e.g. oral chronic GVHD is suspected)
- Oral photographs (optional)
- Oral lesion documentation
- Research blood sample collection
- Saliva sample collection
- Blood pressure

## **6.6 Compliance**

Subject adherence to the trial interventions will be estimated by measuring the dexamethasone levels at time of analysis (the end of study assessment). Subject adherence to the trial interventions will be estimated by self-reporting compliance and the refill of study medication.

## **6.7 Data and Records Management**

### **6.7.1 Records to be kept**

Each study subject will be assigned a study number and individual record. Individual study records will be held in PIs office. Subject ID number will be used in all computer database records and data analysis procedures for the reasons of confidentiality.

### **6.7.2 Data management**

The PI will be responsible for overseeing entry of data into an in-house password protected electronic system and ensuring data accuracy, consistency and timeliness. The principal investigator, associate investigators/research nurses and/or a contracted data manager will assist with the data management efforts. All human subjects personally identifiable information (PII) as defined in accordance to the Health Insurance Portability and Accountability Act, eligibility and consent verification will be recorded in DIR's

Clinical Data System (CDS) or the Laboratory of Cardiac Energetics (LCE) database. Primary data obtained during the conduct of the protocol will be kept in secure network drives or in approved alternative sites that comply with NIH security standards. Primary and final analyzed data will have identifiers so that research data can be attributed to an individual human subject participant, e.g., study-specific identifying number (SSPIN) generated by CDS or other unique code, or minimum PII required for subject identification.

Study data will be stored on the P drive, the Hematology Branch, secure, limited access drive.

**End of study procedures:** Data will be stored in locked cabinets and in a password protected database until it is no longer of scientific value. At the completion of the study the data will be analyzed by the study statistician.

**Loss or destruction of data:** Should we become aware that a major breech in our plan to protect subject confidentiality and trial data has occurred, the IRB will be notified.

**Publication policy:** Given the research mandate of the NIH, subject data including the results of testing and responses to treatment will be entered into an NIH-authorized and controlled research database. Any future research use will occur only after appropriate human subject protection institutional approval such as prospective NIH Intramural IRB review and approval or an exemption from the NIH Office of Human Subjects Research (OHSR).

#### 6.7.3 Quality assurance

Quality assurance will be provided through ongoing review of records for data quality, completeness of consent forms, and completion of study procedures. Monthly meeting of the investigators on the protocol will be scheduled to ensure continued compliance with the study objectives.

#### 6.7.4 Subject confidentiality

All laboratory specimens, evaluation forms, reports, photographs, and other records that leave the site will be identified only by the Study Identification Number (SID) to maintain subject confidentiality. All records will be kept in the subject's medical record. Clinical information will not be released without written permission of the subject, except as necessary for monitoring by the IRB, NHLBI, FDA, or the DSMB.

#### 6.7.5 Publications and research findings

Publication of the results of this trial will be governed by the policies and procedures of NIH. Any presentation, abstract, or manuscript will be made available for review by NHLBI/NCI prior to submission.

### 7. ANCILLARY EXPLORATORY LABORATORY RESEARCH STUDIES

#### 7.1 Collecting, Tracking and Disposition of Samples

**Sample collection:** During the course of participating on this study (screening appointment, follow-up visits, end of study visit, and at the time of development of chronic oral chronic GVHD) blood and saliva will be collected for correlative laboratory research studies. Oral mucosal tissue collection may be performed at baseline, completion of intervention and/or development of oral chronic GVHD, and end of study (6 months after completion of the intervention/12 months post-transplant) and will be collected in the presence of clinical GVHD. Half of the tissue collected will be sent to the department of pathology for

routine H&E staining and the other half will be snap frozen in liquid nitrogen and stored at -80°C for research use.

**Intended use:** These research specimens will not be read by a pathologist or used for diagnostic purposes. Studies will not be used in assessing the primary endpoint, but are undertaken for descriptive or exploratory ancillary research.

**Storage:** Research samples will be stored with identifiers in the secure laboratory of [name].

**Tracking:** Samples will be ordered and tracked through the CRIS research screens. Should a CRIS screen not be available, the NIH form 2803-1 will be completed and will accompany the specimen and be filed in the medical record. In order to ensure proper tracking across several labs, the progress note detailing the consent process will also detail the laboratory to which the sample was initially sent. Specimens will be entered in the NHLBI Biospecimen Inventory System (BSI). Samples will not be sent outside NIH without IRB notification and an executed MTA.

**End of study procedures:** Samples from consenting subjects will be stored until they are no longer of scientific value or if a subject withdraws consent for their continued use, at which time they will be destroyed.

**Loss or destruction of samples:** Should we become aware that a major breech in our plan for tracking and storage of samples has occurred, the IRB will be notified.

